4.3. Subject Participation

Subject participation involves a minimum of five clinic visits at Week 4, Week 12, Week 24, Week 36 and Week 52 of treatment. There will be three phone visits conducted at Weeks 18, 30 and 44. (For Cohort-Week 24, subject participation involves a minimum of three clinic visits at Week 4, Week 12 and Week 24 of treatment. There will be one phone visit conducted at Week 18). The Day 1 visit of this study will be Week 4 of the ARQ-151-311 or ARQ-151-312 or ARQ-151-315 study. The baseline value for safety and efficacy will be the last observation prior to the first dose of ARQ-151 cream in either the ARQ-151 preceding study (ARQ-151-311 or ARQ-151-312 or ARQ-151-315), or this study. The anticipated maximum duration of subject participation is about 24 or 52 weeks. Subjects in the ARQ-151-311 or ARQ-151-312 or ARQ-151-315 study that choose to participate in the long-term extension study will transition directly into the ARQ-151-313 study at the Day 1 visit (Week 4 of Study ARQ-151-311 or ARQ-151-312 or ARQ-151-315).

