5.2.1. Validated Investigator Global Assessment scale for Atopic Dermatitis

Validated Investigator Global Assessment scale for Atopic Dermatitis (vIGA-AD) assessments should be completed prior to other physician assessments.

vIGA-AD assessment will be performed according to the Schedule of Visits and Assessments ([Section 1.3](#)). The vIGA-AD is a static evaluation of qualitative overall AD severity. This global assessment scale is an ordinal scale with five severity grades (reported only in integers of 0 to 4). Each grade is defined by a distinct and clinically relevant morphologic description that minimizes inter-observer variability (see [Appendix 5](#)). vIGA-AD is evaluated for the entire body except the scalp, palms, and soles.

Note: All atopic dermatitis lesions on a subject will be treated including the face, trunk, genitals/skin folds, or limbs (excluding the scalp). The palms and soles will be treated but will not be counted towards any measurements of efficacy (EASI, vIGA-AD, BSA).

Every effort must be made for the same Evaluator to complete the IGA for the subject at every study visit.

IGA will be assessed at clinic visits.

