5.4. Final Study Visit – End of Study

The approximate final study visit will occur at Week 52, except for subjects in the Cohort-Week 24, where the final study visit will occur at Week 24. The procedures performed during this visit are as described in the Schedule of Visits and Assessments ([Section 1.3](#)). A 7-day scheduling window is allowed for this visit. Adverse events will be recorded as reported by the participant or and followed to resolution or stabilization (as necessary).

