5.5 Derived Variables

All questionnaire scores will be derived by Biostatistics in the ADaM datasets using the formulas defined below, even if calculated scores are present in the EDC database. All pre-calculated scores will be ignored for analysis.

- With the following exception, vIGA-AD Score of Clear (0) or Almost Clear (1) = vIGA-AD of ‘Clear’ (0) or ‘Almost Clear’ (1). The exception is that for subjects who discontinued early from study due to an AE or lack of efficacy, the subject will be considered as not having a vIGA-AD score of Clear (0) or Almost Clear (1) for all pre-specified analysis visits (refer to Section 5.4) for which the subject’s day of last dose falls within or is before the start of the analysis visit window.
- With the following exception, vIGA-AD Success = vIGA-AD of ‘Clear’ (0) or ‘Almost Clear’ (1) plus at least a 2-grade improvement from baseline. The exception is that for subjects who discontinued early from study due to an AE or lack of efficacy, the subject will be considered as not having a vIGA-AD success for all pre-specified analysis visits (refer to Section 5.4) for which the subject’s day of last dose falls within or is before the start of the analysis visit window. vIGA-AD Success will be derived for both the Primary and OLE baselines (refer to Section 5.2)
- Date of last contact = the latest of last study visit date, last dose date, end-of-study date and end-of-treatment date.
- Post-OLE Week 4 study duration (days): The duration can be represented as End Date – Start Date +1. The start date of the Post-OLE Week 4 interval will be the date of the OLE Week 4 visit or OLE Day 29 if the subject missed the OLE Week 4 visit. The end date will be the date of last contact. This endpoint will be calculated only for subjects who enter the post-OLE Week 4 study period.
- Duration (days) of the first BIW dosing will be calculated from the first BIW dosing to the start of the succeeding QD dosing interval. Subject’s last contact date will be used to censor

 Innovaderm Research	STATISTICAL ANALYSIS PLAN, Final Version 1.0
Protocol Number: ARQ-151-313	Sponsor: Arcutis Biotherapeutics, Inc.

this endpoint (time-to-event analysis) or as the end date of this duration (analyzed as a continuous endpoint) for subjects who do not revert to a QD dosing regimen after the first BIW dosing. This endpoint will be calculated only for subjects who enter the post-OLE Week 4 study period with at least one BIW dosing interval.

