- Cumulative time (days) on BIW dosing: Subjects may have more than 1 BIW dosing interval. The duration of succeeding BIW dosing intervals will be derived in a manner similar to the first and durations will be summed across all intervals for a subject. This endpoint will be calculated only for subjects who enter the post-OLE Week 4 study period with at least one BIW dosing interval.
- Percent of time on BIW dosing: The cumulative time (days) on BIW dosing will be divided by the Post-OLE Week 4 study duration and multiplied by 100 to measure the percentage of study days on BIW dosing. This endpoint will be calculated only for subjects who enter the post-OLE Week 4 study period with at least one BIW dosing interval.
- Duration (days) of first disease control will be calculated from the first disease control to the time subjects revert to a QD dosing or have a vIGA-AD score ≥ 2 , whichever comes first. Disease control is defined as achievement of a vIGA-AD score of 0, a switch to BIW dosing, and maintenance of a vIGA-AD score of 0 or 1. Disease control starts with the later date of a vIGA-AD score of Clear (0) on or after OLE Week 4 and the switch to BIW dosing. Subject's last contact date will be used to censor this endpoint (time-to-event analysis) or as the end date of this duration (analyzed as a continuous endpoint) for subjects who never lose disease control after the start of the first disease control interval. This endpoint will be calculated only for subjects who enter the post-OLE Week 4 study period and had at least one disease control interval.
- Cumulative time (days) with disease control. Subjects can come in and out of disease control. The duration for each interval will be derived as described above for the first interval. Cumulative time with disease control will sum the durations for all intervals where disease was under control as defined in the previous bullet. This endpoint will be calculated only for subjects who enter the post-OLE Week 4 study period and had at least one disease control interval.
- Percent of time with disease control. The cumulative time with disease control will be divided by the Post-OLE Week 4 study duration and multiplied by 100 to express cumulative time as a percentage of the duration of time that each subject spent in the study after OLE Week 4. This endpoint will be calculated only for subjects who enter the post-OLE Week 4 study period and had at least one disease control interval.

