 Innovaderm Research ■■■	STATISTICAL ANALYSIS PLAN, Final Version 1.0
Protocol Number: ARQ-151-313	Sponsor: Arcutis Biotherapeutics, Inc.

- Duration (days) of the first vIGA-AD of Clear (0) will be calculated from the first vIGA-AD score of 0 during the study to the next vIGA-AD score > 0. Subject's last contact date will be used to censor this endpoint (time-to-event analysis) or as the end date of this duration (analyzed as a continuous endpoint) for subjects who never revert to a vIGA-AD score > 0. This endpoint will be calculated only for subjects who had at least one vIGA-AD score of Clear (0) interval.
- Cumulative time (days) with vIGA-AD of Clear (0). Subjects can have more than 1 vIGA-AD of Clear (0) interval. The duration for each interval will be derived as described above for the first interval. Cumulative time with vIGA-AD of 0 will sum the durations for all intervals. This endpoint will be calculated only for subjects who had at least one vIGA-AD score of Clear (0) interval.
- Percent of time with vIGA-AD of Clear (0). The cumulative time will be divided by the study duration and multiplied by 100 to express cumulative time as a percentage of the duration of time that each subject spent in the study. This endpoint will be calculated only for subjects who had at least one vIGA-AD score of Clear (0) interval.
- Duration (days) of the first vIGA-AD of Clear (0) or Almost Clear (1) will be calculated from the first vIGA-AD score of 0 or 1 during the study to the next vIGA-AD score > 1. Subject's last contact date will be used to censor this endpoint (time-to-event analysis) or as the end date of this duration (analyzed as a continuous endpoint) for subjects who never revert to a vIGA-AD score > 1. This endpoint will be calculated only for subjects who had at least one VIGA-AD with a score of Clear (0) or Almost Clear (1) interval.
- Cumulative time (days) with vIGA-AD of Clear (0) or Almost Clear (1). Duration with vIGA-AD score of 0 or 1 measures the duration for the first interval with a VIGA-AD score of 0 or 1. There can be more than 1 interval. Cumulative time with vIGA-AD of 0 or 1 will sum the durations for all intervals. The duration for each interval will be derived as described above for the first interval. This endpoint will be calculated only for subjects who had at least one VIGA-AD with a score of Clear (0) or Almost Clear (1) interval.

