12.3.1 Main Analysis

Missing other efficacy endpoints will not be imputed.

Duration, cumulative time, and percent of time endpoints will be summarized using descriptive statistics by treatment group (refer to Section 5) and two-sided 95% CI of the mean will also be provided.

For duration endpoints, the number and percentage of subjects experiencing a status change or censored will be provided overall and by treatment group, along with reason for censoring. Additionally, these endpoints will also be analyzed using Kaplan–Meier (KM) method. The KM estimates of the time-to-event will be provided overall and by treatment group for the 25th, 50th (median), and 75th percentiles along with their corresponding two-sided 95% CI. The estimates of the SEs will be computed using the Greenwood's formula. The two-sided 95% CI for the survival function at the 25th, 50th, and 75th percentiles will be calculated according to Brookmeyer and Crowley (1982)². KM curves will be provided overall and by treatment group.

Dichotomic, change from baseline, and percent change from baseline endpoints will be summarized similarly as the secondary efficacy endpoints (refer to Section 12.2).

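### KM durations of vIGA-AD 0 and 0/1, and less so of disease control: completers who pass the exit score are normally censored on the day others fail it, which biases the curve down across the exit window and can produce a false late median

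*SAP*

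**What the plan says.** **Event.** Under SAP 5.5, the first vIGA-AD 0 interval runs "from the first vIGA-AD score of 0 during the study to the next vIGA-AD score > 0". The 0/1 interval is built the same way, with a score above 1 as the loss. Disease control ends when subjects "revert to a QD dosing or have a vIGA-AD score" of 2 or more, whichever comes first.

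**Censoring.** For subjects who never lose the state, the subject's "last contact date will be used to censor this endpoint (time-to-event analysis) or as the end date of this duration". SAP 5.5 also gives the definition: "Date of last contact = the latest of last study visit date, last dose date, end-of-study date and end-of-treatment date".

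**Assessment times.** Protocol 5.2.1 states that "IGA will be assessed at clinic visits". Protocol 4.3 requires "a minimum of five clinic visits at Week 4, Week 12, Week 24, Week 36 and Week 52 of treatment"; Cohort-Week 24 has Weeks 4, 12 and 24. The schedule in Protocol 1.3 scores vIGA-AD at the last visit and marks study exit there, with no later visit. Of the final visit, Protocol 5.4 says: "A 7-day scheduling window is allowed for this visit".

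**Output.** SAP 12.3.1 plans KM curves on these actual-day durations: "The KM estimates of the time-to-event will be provided overall and by treatment group for the 25th, 50th (median), and 75th percentiles". SAP 6.6 adds displays by Cohort for all duration endpoints, and a Week 4-start subgroup for BIW dosing and disease control. SAP 12.3.2 plans no sensitivity analysis for them.

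**The concern.** KM assumes that a subject censored at time t has the same future risk as those still under observation. Here that fails at the exit visit. Every subject still in response is tested once. A failer has an event that day, while a passer has just been shown not to have failed and is normally censored that same day. Because exit days differ between subjects, someone who passes early in the window no longer counts in the denominator when another subject fails later in it. One round of testing is treated as a run of daily hazards on a dwindling group.

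The KM quartiles and medians are read as evidence on how long response lasts. A median produced this way mainly reflects the length of follow-up, and it understates durability. The bias also runs opposite to the more familiar one, in which losses between visits are dated late, so the two should not be assumed to cancel.

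**Working it through.** The plan states no loss rate, median or event count for these endpoints, so there is no figure to reproduce.

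**Inputs from the documents:** target days 29, 85, 169, 253 and 365 (SAP Table 3); windows of ±3 days at Week 4 and ±7 days later (Protocol 1.3).

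**Assumptions:** a constant probability p of loss per clinic visit; visit days uniform within their windows; no dropout; last contact on the exit visit; first interval starting at Week 4.

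**1. Size of the exit step.** If exits spread evenly over 15 days, the group still to exit falls from 15 parts to 1. KM multiplies the curve by the product over k = 1 to 15 of (1 − p/k); the true factor is 1 − p. Duration is exit day minus start day, so the ±3-day start window widens the spread to 15 + 7 − 1 = 21 days. With weight w_d on day d, the factor becomes the product over d of [1 − p·w_d / (sum of w from d onward)].

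| p | true 1 − p | KM, exit window only | KM, with start window |
|---|---|---|---|
| 0.05 | 0.95 | 0.85 | 0.79 |
| 0.10 | 0.90 | 0.71 | 0.62 |
| 0.15 | 0.85 | 0.60 | 0.48 |
| 0.20 | 0.80 | 0.50 | 0.37 |

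A ±2-day spread is already enough to matter. At p = 0.15, 0.85 × 0.925 × 0.95 × 0.9625 × 0.97 = 0.70, a 30% step instead of 15%.

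**2. End of the curve.**
- Cohort-Week 24, p = 0.15 (tests at Weeks 12 and 24): true 0.85² = 0.72; planned KM about 0.85 × 0.48 = 0.41.
- Cohort-Week 52, p = 0.10 (tests at Weeks 12, 24, 36 and 52): true 0.90⁴ = 0.66; planned KM about 0.90³ × 0.62 = 0.45.

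**3. Simulation, n = 300.**
- Cohort-Week 24, p = 0.15: 0.42 against 0.72. A median appears in 68% of runs, at about 149 days; with nominal dating, in none.
- Cohort-Week 52, p = 0.10: 0.45 against 0.66. A median appears in 54% of runs, at about 345 days; with nominal dating, in none.

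Nominal Week 4-to-exit durations are 169 − 29 = 140 and 365 − 29 = 336 days. With both windows the maximum is 10 days more, 150 and 346, so these medians sit at the very end of the exit spread.

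**4. Last contact after the exit visit** (Cohort-Week 52, p = 0.12, n = 200; true end survival 0.60). End survival is 0.37 at lag 0, 0.46 at 1 day, 0.54 at 3, 0.58 at 7 and 0.60 at 14. The share of runs with a median falls from 83% to 65%, 21%, 4% and 1%.

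**5. Disease control.** Phone-in returns to QD are dated between visits and carry no exit-visit test, so the effect is diluted. With p = 0.02–0.06 for vIGA-AD of 2 or more and a phone-return hazard of 0.0008/day (both assumed; Week 4 starters, Cohort-Week 52), end survival is 0.48–0.65 against 0.60–0.70. A median appears in 5–42% of runs, against none with nominal timing.

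**The case against.** **Last contact need not be the exit visit.** It is the latest of four dates, and the documents do not define the end-of-study date or say that it equals the exit visit. This stands. A reader might infer that the problem disappears only if every exit falls on one day. That is wrong: a lag also removes it (step 4), and in the two step 3 cases a 3-day lag cut the false-median rate to 0–1%. But nothing in the SAP requires a lag, and with no later visit scheduled the dates normally coincide.

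**The size rests on assumed rates.** This also stands. At p = 0.05 a false median appears in only 5–7% of runs, although the exit step is still too large (0.79 against 0.95). At p = 0.20 in Cohort-Week 52 the median is real (true survival 0.80⁴ = 0.41) and only the tail is too low. The plan can produce a false median; the documents do not show that it will.

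**A careful reader would notice.** SAP 12.3.1 also reports counts of losses and censorings, reasons for censoring, confidence intervals and full curves. In the step 3 cases the median arises with about 8–9 subjects at risk, beside a table showing that roughly 72% or 66% never lost response. That helps, but a reported median is likely to be quoted without it.

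**These are minor endpoints.** They are descriptive other-efficacy endpoints in a safety study with no hypothesis tests. A reader might take them as the study's whole evidence on maintenance. The documents do not support that: BIW duration has no exit-visit test, and the by-visit vIGA-AD secondary endpoints do not use KM. Both are unaffected.

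**Conclusion.** The point holds for the KM analyses of vIGA-AD 0 and 0/1 duration, and more weakly for disease control. When last contact is the exit visit, censoring depends on the exit score, and the curve is biased down across the exit window. With 10–15% loss per visit and Week 4 starts, end survival is about 0.42–0.45 where 0.66–0.72 is correct. The effect is clearest where exit durations align, as in the by-Cohort displays and, for disease control, the Week 4-start subgroup. Mixed start visits spread exits over several durations, with the strongest drop at the last cluster. It warrants correction because the planned medians can mislead and the change is cheap, but it does not affect the primary or secondary endpoints.

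**What to change.** In SAP 5.5 and 12.3.1, for the KM analyses only:

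- **vIGA-AD 0 and 0/1:** date scheduled-visit starts and losses, and the censoring of completers, at the nominal visit day (29, 85, 169, 253, 365). Exit failures and exit censorings then tie, and KM counts censored subjects as at risk at a tie; in simulation this recovers the true value. Keep actual dates for losses found at unscheduled visits outside the protocol window, capped at the nominal exit day. Table 3 windows should not be used to move them: a loss on Day 310 would shift by 365 − 310 = 55 days.
- **Disease control:** do the same and keep actual dates for phone-in QD returns, but set any return after the nominal exit day to that day. The cap is essential. Without it a late return can fall after all completers are censored, and KM reached zero in 36% of Cohort-Week 24 runs (p = 0.02, hazard 0.0012/day). An interval-censored estimator is an alternative.
- **If actual dates are kept:** report no KM percentile beyond the earliest duration at which final-visit assessments begin. For Week 4 starters that is (169 − 7) − (29 + 3) = 130 days in Cohort-Week 24 and (365 − 7) − 32 = 326 days in Cohort-Week 52. With mixed starts it comes much sooner: a Week 12 start in Cohort-Week 24 gives (169 − 7) − (85 + 7) = 70 days.

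The cost is SAP wording and one date derivation. Scheduled-visit event times are rounded by up to 7 days.

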- SCORAD Total Score = [Overall BSA affected by AD / 5] + [Intensity score * 7/ 2] + Subjective symptoms score (i.e., pruritus + sleep loss), ranging from 0 to 103. SCORAD total score will be set to missing if information for any of the three measures is missing.
- Change from baseline = Assessment value at post-baseline visit X – baseline value.
- Percent change from baseline = (Assessment value at post-baseline visit X – baseline value) × 100% / (baseline value)

Percent change from baseline will be missing in situation where baseline value equals to 0.

- Exposure-adjusted incidence rate (EAIR) = (number of subjects with an event / total within-arm exposure [days]) * 365.25 days/year * 100.
- BMI (kg/m²) = (weight in kg)/ [(height in cm/100)²]. For child and adolescent (2 to 17 years), after BMI is calculated, it is expressed as a percentile using data files and instructions provided by the CDC (https://www.cdc.gov/growthcharts/percentile_data_files.htm).

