5.6 Descriptive Statistics

All continuous variables will be summarized by presenting the number of subjects ('n'), mean, standard deviation (SD), median, Q1, Q3, minimum, and maximum. For PK endpoints, the coefficient of variation (CV), geometric mean, and geometric CV will also be provided.

Categorical variables will be presented as frequencies and percentages. The AE tables will also present the within-arm summary measure of EAIR; expressed as number of subjects with events per 100 subject exposure years.

 Innovaderm Research 	STATISTICAL ANALYSIS PLAN, Final Version 1.0
Protocol Number: ARQ-151-313	Sponsor: Arcutis Biotherapeutics, Inc.

Summary tables will be presented by visit, when applicable, and treatment group (refer to Section 5).

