11 STUDY TREATMENT EXPOSURE AND TREATMENT COMPLIANCE

A summary of exposure to study treatment will be presented using the safety population by treatment group as defined in Section 5. It will include descriptive statistics on the number of days on OLE study treatment, as well as the number of study treatment applications based on diary, for each treatment group. Since subjects in the roflumilast arm of their parent study will simply be continuing the same treatment, their first treatment date will be the date of their week 4 visit in the parent study, even if study drug application was interrupted on that date. The number of days on study treatment in OLE study, will be calculated as follows:

$$(\text{Last treatment date in OLE} - \text{First treatment date in OLE}) + 1$$

For each subject, compliance (%) with study treatment will be calculated as follows:

$$\frac{\text{Number of study treatment applications}}{\text{Number of expected study treatment applications}} \times 100$$

Applied dose count and missed dose applications count were collected in eCRF study drug interruption module. Number of study treatment applications will be calculated as the sum of applied dose count.

Number of expected study treatment applications will be calculated as the sum of number of investigational product applications and number of doses missed. Of note, number of expected study treatment applications might change during the course of the study (refer to Section 3.1 for more details).

The number and percent of subjects who switch to a maintenance dosing schedule (BIW) at least once after week 4 will be provided by treatment group. The cumulative time and percent of time (Section 5.5) on the maintenance dosing schedule will be summarized only for those subjects who switched to BIW dosing at least once. The percent of time on the maintenance dosing schedule will also be summarized categorically as]0-25%],]25-50%],]50-75%], and >75%. The number of times each subject returned to QD dosing after switching to BIW dosing will be summarized categorically.

Subjects who roll over from the ARQ-151-315 study and turn 6 years old during the study will switch to Roflumilast cream 0.15% at their first scheduled post-birthday visit. The percentage of study days spent on each dose in this study will be summarized.

 Innovaderm Research ■■■	STATISTICAL ANALYSIS PLAN, Final Version 1.0
Protocol Number: ARQ-151-313	Sponsor: Arcutis Biotherapeutics, Inc.

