13.1 Adverse Events

AEs will be coded according to the latest available version of MedDRA (Version 25.0 or higher).

A treatment emergent adverse event (TEAE) is defined as an AE that started post application of study medication at the Day 1 visit of study ARQ-151-313 or was present at treatment initiation but worsened during treatment, through study completion. See [Appendix 2](#) for handling of completely or partially missing dates for AEs. In the case where it is not possible to define an AE as treatment emergent or not, the AE will be classified as treatment emergent.

An overall summary of TEAEs will be presented by treatment group as defined in Section 5, which will include the total number of events, and the number and percentage of subjects who experienced at least one TEAE, TEAE by the maximum severity, TEAE by relationship and TEAE by the strongest relationship, treatment-emergent SAE, treatment-emergent Non-SAE, TEAE leading to study treatment discontinuation, TEAE leading to study discontinuation, TEAE on an application site, and TEAE leading to death. In addition, similar summary as described above will be presented by age group (refer to Section 6.6) for rollovers from study ARQ-151-311/312.

The number and percentage of subjects who experience at least one TEAE will be summarized by SOC, PT, and treatment group as defined in Section 5. A subject experiencing the same TEAE multiple times within the same PT will be counted only once for that PT. Similarly, a subject experiencing the same TEAE multiple time within the same SOC will be counted only once for

 Innovaderm Research	STATISTICAL ANALYSIS PLAN, Final Version 1.0
Protocol Number: ARQ-151-313	Sponsor: Arcutis Biotherapeutics, Inc.

that SOC. TEAEs will be sorted alphabetically by SOC and within each SOC, the PT will be presented by descending frequency. In addition, similar summary as described above will be presented by age group (refer to Section 6.6) for rollovers from study ARQ-151-311/312.

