The number and percentage of subjects who experience at least one TEAE will also be summarized by SOC, PT, strongest relationship with study treatment (related or not related) and treatment group. A treatment-related TEAE is defined as any TEAE that is assessed by the Investigator as likely, probably, or possibly related to study treatment. TEAE that is assessed as unrelated or unlikely will be defined as not treatment-related. If a subject experiences more than one TEAE within different relationship categories within the same SOC/PT, only the worst case (the strongest relationship) will be reported. TEAE with an unknown relationship will be considered as treatment-related.

The number and percentage of subjects who experience TEAE will also be summarized by SOC, PT, maximum severity (mild/moderate/severe/life threatening/death related to AE), and treatment group as defined in Section 5. If a subject experiences more than one TEAE within different severity categories within the same SOC/PT, only the worst case (the maximum severity) will be reported. TEAE with an unknown severity will be considered as severe.

The number and percentage of subjects who had treatment-emergent SAE will be summarized by SOC, PT, and treatment group as defined in Section 5. TEAEs leading to study drug discontinuation and TEAEs leading to study discontinuation will be summarized similarly.

Frequency and percentage of subjects who experience TEAE on an application site will be summarized by SOC, PT, and treatment group as defined in Section 5.

A plot of most frequent TEAE ($\geq 1\%$) will be provided by PT and treatment group as defined in Section 5 (overall TEAE and overall treatment-emergent SAE will be included in the same plot).

The EAIR and the corresponding 95% CI will be reported for all tables of TEAEs by SOC and PT described earlier in this section. The EAIR per 100-pt year, defined in Section 5.5, will be calculated in each arm and the 95% CI will be calculated by using a Poisson regression model with number of TEAEs as dependent variable and log of exposure time as offset. Additionally, the difference in EAIR between the 'Roflumilast cream 0.15%' and 'Vehicle / Roflumilast cream 0.15%' treatment groups (refer to Section 5) will be provided along with the associated two-sided 95% CI.

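### The EAIR divides first-event subjects by exposure that continues after the event, so for common adverse events it understates the incidence rate and varies with length of follow-up

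*SAP*

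**What the plan says.** SAP 5.5 gives the formula as ("number of subjects with an event / total within-arm exposure [days"]), multiplied by 365.25 and by 100. SAP 5.6 puts the same measure in words: "expressed as number of subjects with events per 100 subject exposure years".

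For the numerator, SAP 13.1 states: "A subject experiencing the same TEAE multiple times within the same PT will be counted only once for that PT". It applies the same rule to SOCs.

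For the denominator, the only definition of exposure days is in SAP 11: last minus first OLE treatment date, plus one. Neither section ends a subject's exposure at an event.

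SAP 13.1 requires the EAIR and a 95% CI in every table of TEAEs by SOC and PT described there, which includes the age-group table for ARQ-151-311/312 rollovers. The CI comes from a "Poisson regression model with number of TEAEs as dependent variable and log of exposure time as offset". The section also plans "the difference in EAIR between the 'Roflumilast cream 0.15%' and 'Vehicle / Roflumilast cream 0.15%' treatment groups", with a CI.

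**The concern.** A subject with an event in Week 2 has already added the one count that he or she can add to that row, yet stays in the denominator for up to 50 more weeks. Time at risk of a first event ends at that event. With a common follow-up time, the formula reduces to the incidence proportion divided by follow-up time, which falls as follow-up lengthens even if the risk never changes.

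An exposure-adjusted rate is meant to put subjects with different follow-up on one scale, and this study mixes 24-week and 52-week subjects. Two planned outputs set unequal follow-up side by side:

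- **Age groups.** Cohort-Week 24 takes only ages 6-17, while adults are followed for 52 weeks.
- **Interim and final.** SAP 6.3 runs all planned analyses at the interim, on data up to an earlier cut-off. EAIRs for common events would then drift down by the final analysis with no change in risk.

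The Poisson model adds a second mismatch. Its outcome is the number of TEAEs, whereas the EAIR counts subjects, so the CI may belong to a different quantity from the estimate beside it.

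**Working it through.** The documents state no EAIR, adverse event rate or precision target, so there is no figure to reproduce.

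**Inputs**
- Follow-up T: 168 days (24 weeks) or 364 days (52 weeks), from SAP 3.1.
- 52-week incidence p: not in the documents; assumed at 5%, 20% and 40%.
- Constant hazard and no dropout: assumed, then varied below.

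**Formulas**
- Daily hazard: λ = -ln(1 - p) / 364
- First-event rate per 100 years: λ × 36,525
- SAP EAIR: (1 - exp(-λT)) / T × 36,525
- Ratio of SAP EAIR to first-event rate: (1 - exp(-λT)) / (λT)

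**Worked case, p = 40%**
- λ = 0.51083 / 364 = 0.0014034 per day, so the first-event rate is 51.26.
- 24 weeks: λT = 0.2358 and 1 - exp(-0.2358) = 0.2100. The EAIR is 0.2100 / 168 × 36,525 = 45.66, which is 10.9% low.
- 52 weeks: 0.4000 / 364 × 36,525 = 40.14, which is 21.7% low.

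| 52-week incidence | First-event rate | SAP EAIR, 24 weeks | SAP EAIR, 52 weeks |
|---|---|---|---|
| 5% | 5.15 | 5.09 (-1.2%) | 5.02 (-2.5%) |
| 20% | 22.39 | 21.28 (-5.0%) | 20.07 (-10.4%) |
| 40% | 51.26 | 45.66 (-10.9%) | 40.14 (-21.7%) |

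At 40%, a 24-week group and a 52-week group with the same hazard differ by 45.66 / 40.14 = 1.14, or 14%, through follow-up alone. The planned age contrast would show less than this, because 6-17-year-olds enrolled before Amendment 1 are followed for 52 weeks.

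**Does this depend on the constant hazard?** The direction does not. For common follow-up T the ratio is the average of the event-free survival function over 0 to T, which is at most 1 and cannot rise with T. With a front-loaded hazard (Weibull, shape 0.5) and p = 40%, the shortfall is 20.4% at 24 weeks and 28.3% at 52 weeks. A simulation with a constant hazard and an assumed 20% yearly dropout gave 10.7% and 21.0%.

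**Planned group difference.** If both prior-treatment groups have the same hazard and the same cohort mix, the true difference is zero and the EAIR difference is also zero. If true rates differ, the difference is compressed. Take hypothetical rates of 50 and 75 per 100 years, a true difference of 25, and an assumed mix in each group of 550 subjects at 24 weeks to 300 or to 600 at 52 weeks:
- 550:300 gives 57.7 - 41.8 = 15.9.
- 550:600 gives 56.0 - 41.0 = 15.0.

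At 5 against 7.5 per 100 years (true difference 2.5), the same mixes give 2.39 and 2.37, a loss of about 5%.

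**The case against.** The study is descriptive: SAP 5.7 plans no hypothesis tests. The protocol's primary analysis tabulates TEAEs and SAEs by PT and SOC, and those counts and percentages do not change. The EAIR is a SAP addition that no decision rule uses. SAP 5.6 labels it as what it computes, so it is low only against a first-event rate that the SAP never says it estimates. The larger shortfalls rest on assumed incidences, and SAP 13.1 requires EAIRs by SOC and PT without naming an any-TEAE row.

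Most of this stands and limits the severity. It does not remove the point, because a measure called exposure-adjusted should not move with follow-up at constant risk, and here it appears in tables where follow-up differs.

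Three stronger inferences are not supported:

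- **A single shortfall for all of the approximately 1500 subjects.** SAP 5 reports ARQ-151-311/312 and ARQ-151-315 rollovers separately, so no planned column pools them.
- **A distorted 24-week against 52-week safety comparison.** SAP 3.6 and 6.6 plan no by-cohort adverse event tables.
- **A prior-treatment difference roughly halved.** Rates of 50 and 75 with everyone at 52 weeks give 52.8 - 39.4 = 13.4, but the groups compared contain all the 24-week subjects. Both groups also receive the 0.15% cream in this study, and nothing in the documents suggests that their rates differ by that much.

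**Conclusion.** The point holds at moderate weight. As defined, the EAIR never exceeds the first-event incidence rate, and for common rows it falls short by an amount that grows with follow-up. At PTs of about 5% or less the effect is 1-3% under a constant hazard, so it is negligible for uncommon PTs and, in all likelihood, for most SAEs. At assumed incidences of 20-40% it is 5-11% at 24 weeks and 10-22% at 52 weeks. That range is relevant to SOC totals, the commonest PTs, and any TEAE if an EAIR is shown for it.

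The outputs most exposed are the age-group tables for ARQ-151-311/312 rollovers and any reading of interim against final EAIRs. The prior-treatment difference is affected if true rates, or the cohort mix, differ between the groups.

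The sizes depend on the assumed incidences and hazard shape. The shortfall is smaller where the event itself ends treatment. That post-event time is included is read from the formula and the absence of a truncation rule; the SAP does not say so in words.

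**What to change.** Change the denominator and the Poisson outcome together. Truncating time while still modelling all events would put repeat events over first-event time and overstate the rate.

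1. **SAP 5.5.** Define EAIR = 100 × 365.25 × (subjects with at least one event in the row) / (sum of days at risk). Days at risk run from the first OLE dose to the first event in that row or, with no event, to the end of the TEAE/exposure period. State that end date.
2. **SAP 13.1.** Use a 0/1 outcome per subject (at least one event in the row) with log days at risk as offset. Take the CI and the group difference from these same quantities.
3. **If an event rate is also wanted,** report the number of TEAEs over full exposure separately, under its own label.

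The cost is a short SAP revision and row-specific denominators in the adverse event programs. No new data are needed. EAIRs for common events will come out somewhat higher.
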